8.3 Emergency unblinding of treatment assignment

Not applicable. This is an open-label study.

8.4 Pregnancies

To ensure patient safety, each pregnancy occurring while the patient is on study treatment must be reported to Novartis within 24 hours of learning of its occurrence. The pregnancy should be followed up to determine outcome, including spontaneous or voluntary termination, details of the birth, and the presence or absence of any birth defects, congenital abnormalities, or maternal and/or newborn complications.

Pregnancy should be recorded on a Clinical Trial Pregnancy Form and reported by the investigator to the oncology Novartis Drug Safety and Epidemiology Department (DS&E). Pregnancy follow-up should be recorded on the same form and should include an assessment of the possible relationship to panobinostat of any pregnancy outcome. Any SAE experienced during pregnancy must be reported on the SAE Report Form.

Pregnancy outcomes must be collected for the female partners of any males who took study treatment in this study. Consent to report information regarding these pregnancy outcomes should be obtained from the mother. The collection of this information could last for up to 12 months following the birth of the child. The Study Doctor and Novartis may decide what pertinent information is collected as necessary or indicated based on the study.

8.5 Warnings and precautions

No evidence available at the time of the approval of this study protocol indicated that special warnings or precautions were appropriate, other than those noted in the provided Investigator Brochure. Additional safety information collected between [Investigator Brochure] updates will be communicated in the form of Investigator Notifications. This information will be included in the patient informed consent and should be discussed with the patient during the study as needed.

8.6 Data Monitoring Committee

Not applicable.

8.7 Steering Committee

Not applicable.

9 Data collection and management

9.1 Data confidentiality

Information about study subjects will be kept confidential and managed under the applicable laws and regulations. Those regulations require a signed subject authorization informing the subject of the following:

- What protected health information (PHI) will be collected from subjects in this study
- Who will have access to that information and why
- Who will use or disclose that information
- The rights of a research subject to revoke their authorization for use of their PHI.

In the event that a subject revokes authorization to collect or use PHI, the investigator, by regulation, retains the ability to use all information collected prior to the revocation of subject authorization. For subjects that have revoked authorization to collect or use PHI, attempts should be made to obtain permission to collect follow-up safety information (e.g. has the subject experienced any new or worsened AEs) at the end of their scheduled study period.

The data collection system for this study uses built-in security features to encrypt all data for transmission in both directions, preventing unauthorized access to confidential participant information. Access to the system will be controlled by a sequence of individually assigned user identification codes and passwords, made available only to authorized personnel who have completed prerequisite training.

9.2 Site monitoring

Before study initiation, at a site initiation visit or at an investigator's meeting, Novartis personnel (or designated CRO) will review the protocol and CRFs with the investigators and their staff. During the study, the field monitor will visit the site regularly to check the completeness of patient records, the accuracy of entries on the CRFs, the adherence to the protocol to Good Clinical Practice, the progress of enrollment, and to ensure that study treatment is being stored, dispensed, and accounted for according to specifications. Key study personnel must be available to assist the field monitor during these visits.

[figure not shown]
The investigator must maintain source documents for each patient in the study, consisting of case and visit notes (hospital or clinic medical records) containing demographic and medical information, laboratory data, electrocardiograms, and the results of any other tests or assessments. All information recorded on CRFs must be traceable to source documents in the patient's file. The investigator must also keep the original signed informed consent form (a signed copy is given to the patient).

The investigator must give the monitor access to all relevant source documents to confirm their consistency with the CRF entries. Novartis monitoring standards require full verification for the presence of informed consent, adherence to the inclusion/exclusion criteria and documentation of SAEs. Additional checks of the consistency of the source data with the CRFs are performed according to the study-specific monitoring plan.

9.3 Data collection

For studies using Electronic Data Capture (EDC), the designated investigator staff will enter the data required by the protocol into the Electronic Case Report Forms (eCRF). The eCRFs have been built using fully validated secure web-enabled software that conforms to 21 CFR Part 11 requirements, Investigator site staff will not be given access to the EDC system until they have been trained. Automatic validation programs check for data discrepancies in the eCRFs and, allow modification or verification of the entered data by the investigator staff.

The Principal Investigator is responsible for assuring that the data entered into eCRFs is complete, accurate, and that entry and updates are performed in a timely manner.

9.4 Database management and quality control

For studies using eCRFs, Novartis personnel (or designated CRO) will review the data entered by investigational staff for completeness and accuracy. Electronic data queries stating the nature of the problem and requesting clarification will be created for discrepancies and missing values and sent to the investigational site via the EDC system. Designated investigator site staff are required to respond promptly to queries and to make any necessary changes to the data.

At the conclusion of the study, the occurrence of any protocol violations will be determined. After these actions have been completed and the data has been verified to be complete and accurate, the database will be declared locked and made available for data analysis. Authorization is required prior to making any database changes to locked data, by joint written agreement between the Global Head of Biostatistics and Data Management and the Global Head of Clinical Development.

For EDC studies, after database lock, the investigator will receive a CD-ROM or paper copies of the patient data for archiving at the investigational site.

10 Statistical methods and data analysis

10.1 Analysis sets

The following analysis sets will be used for statistical analysis and data reporting.

10.1.1 Full Analysis Set

Not applicable.

10.1.2 Safety Set

The Safety Set includes all patients who received at least one dose of study medication after enrolling into the roll-over protocol.

10.1.3 Dose-determining analysis set

Not applicable.

10.2 Patient demographics/other baseline characteristics

[figure not shown]
Demographic and other baseline data characteristics will be summarized descriptively for the Safety Set.

10.3 Treatments (study treatment, compliance)

Dose administration data will be summarized using the Safety Set.

10.4 Primary objective

The primary objective is to evaluate long term safety as assessed by the occurrence of AEs/SAEs.

10.4.1 Variable

See [Section 10.5.3](#).

10.4.2 Statistical hypothesis, model, and method of analysis

No hypothesis will be tested.

10.4.3 Handling of missing values/censoring/discontinuations

Not applicable.

10.4.4 Supportive analyses

No supportive analysis will be performed.

10.5 Secondary objectives

10.5.1 Key secondary objective(s)

Not applicable.

10.5.2 Other secondary efficacy objectives

The secondary objective of the study was to evaluate clinical benefit as assessed by the investigator. Proportion of patients with clinical benefit as assessed by the investigator will be summarized at scheduled visits.

10.5.3 Safety objectives

The assessment of safety will be based mainly on the frequency of AEs and SAEs.

10.5.3.1 Analysis set and grouping for the analyses

The overall observation period will be divided into two mutually exclusive segments:

[figure not shown]
1. on-treatment period: from day of first dose of study medication to 30 days after last dose of study medication
2. post-treatment period: starting at day 30+1 after last dose of study medication.

10.5.3.2 Adverse events (AEs)

Summary tables of adverse events (AEs) have to include only AEs that started or worsened during the on-treatment period, the **treatment-emergent** AEs. However, all safety data (including those from the post-treatment periods) will be listed and those collected during the post treatment period are to be flagged.

The incidence of treatment emergent adverse events (new or worsening from baseline) will be summarized by system organ class and/or preferred term, severity (based on CTCAE grades), type of adverse event, relation to study treatment.

Deaths reportable as SAEs and non-fatal serious adverse events will be listed by patient and tabulated by type of adverse event.

10.5.3.3 Other safety data

Not applicable.

10.5.3.4 Tolerability

Not applicable.

10.6 Interim analysis

Not applicable.

10.7 Sample size calculation

Not applicable.

10.8 Power for analysis of key secondary variables

Not applicable.

11 Ethical considerations and administrative procedures

11.1 Regulatory and ethical compliance

This clinical study was designed, shall be implemented and reported in accordance with the ICH Harmonized Tripartite Guidelines for Good Clinical Practice, with applicable local regulations (including European Directive 2001/20/EC and US Code of Federal Regulations Title 21), and with the ethical principles laid down in the Declaration of Helsinki.

[figure not shown]
11.2 Responsibilities of the investigator and IRB/IEC/REB

The protocol and the proposed informed consent form must be reviewed and approved by a properly constituted Institutional Review Board/Independent Ethics Committee/Research Ethics Board (IRB/IEC/REB) before study start. Prior to study start, the investigator is required to sign a protocol signature page confirming his/her agreement to conduct the study in accordance with these documents and all of the instructions and procedures found in this protocol and to give access to all relevant data and records to Novartis monitors, auditors, Novartis Clinical Quality Assurance representatives, designated agents of Novartis, IRBs/IECs/REBs and regulatory authorities as required.

11.3 Informed consent procedures

Eligible patients may only be included in the study after providing written (witnessed, where required by law or regulation), IRB/IEC/REB-approved informed consent

Informed consent must be obtained before conducting any study-specific procedures (i.e. all of the procedures described in the protocol). The process of obtaining informed consent should be documented in the patient source documents. The date when a subject's Informed Consent was actually obtained will be captured in their CRFs.

Novartis will provide to investigators, in a separate document, a proposed informed consent form (ICF) that is considered appropriate for this study and complies with the ICH GCP guideline and regulatory requirements. Any changes to this ICF suggested by the investigator must be agreed to by Novartis before submission to the IRB/IEC/REB, and a copy of the approved version must be provided to the Novartis monitor after IRB/IEC/REB approval.

Women of child bearing potential should be informed that taking the study medication may involve unknown risks to the fetus if pregnancy were to occur during the study and agree that in order to participate in the study they must adhere to the contraception requirement for the duration of the study. If there is any question that the patient will not reliably comply, they should not be entered in the study.

Additional consent form

Not applicable.

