Purpose and rationale	The purpose of this study is to better characterize the long-term safety of single agent panobinostat in patients who are on single agent panobinostat treatment in a Novartis-sponsored, Oncology Global Development & Global Medical Affairs (OGD&GMA) study and are benefiting from the treatment as judged by the investigator.
Primary Objective(s) and Key Secondary Objective	To evaluate long term safety data (SAEs and AEs)
Secondary Objectives	To evaluate clinical benefit as assessed by the investigator
Study design	
This is a multi-center, open label study to better characterize the long-term safety of patients being treated in current Novartis-sponsored Oncology OGD&GMA studies and who are benefiting from treatment with single agent panobinostat. There will be no screening period for this study. Eligible patients are to be consented and can start their treatment with panobinostat as soon as they enter the study. All patients must report to the study site for their first visit at which time, a quarterly supply of panobinostat can be dispensed to the patient. Patients must return to the study center on quarterly (every 12 +/- 2 weeks) basis for resupply of study medication at which time drug dispensing and adverse event information will be collected.
 
Patients will continue to be treated until they are no longer benefiting from panobinostat treatment, develop unacceptable toxicities, withdraw consent, are non-compliant to the protocol (i.e. pregnancy occurs, etc.), the investigator feels it is no longer in the patient's best interest to continue panobinostat therapy or the patient dies, whichever comes first.
 
A patient will reach the end of study when panobinostat treatment is permanently discontinued and the end of treatment visit has been performed. All patients must be followed up for safety evaluations for 30 days after the last dose of study treatment. Following this there are no further follow-up study visits.
 
The study is expected to remain open for 5 years or until such time that enrolled patients no longer need treatment with panobinostat, whichever comes earlier.

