5.3 Exclusion criteria

Patients eligible for this study must not meet **any** of the following criteria:

1. Patient has been permanently discontinued from s.a. oral panobinostat study treatment in the parent study due to unacceptable toxicity, withdrawal of consent, non-compliance to study procedures or any other reason (including progression of disease).
2. Patient has participated in a Novartis sponsored combination trial where panobinostat was dispensed in combination with another study medication and is still receiving combination therapy.
3. Patient is pregnant or nursing (lactating) at time of entry into the roll-over protocol. Pregnancy is defined as the state of a female after conception and until the termination of gestation, confirmed by a positive hCG laboratory test.
4. Women of child-bearing potential and male patients with sexual partner(s) of child-bearing potential unwilling to use highly effective methods of contraception during dosing and for a specified duration (6 months for male participants and 3 months for females) after stopping study treatment.

Highly effective contraception methods include:

- Total abstinence (when this is in line with the preferred and usual lifestyle of the subject. Periodic abstinence (e.g., calendar, ovulation, symptothermal, post-ovulation methods) and withdrawal are not acceptable methods of contraception.
- Female sterilization (have had surgical bilateral oophorectomy with or without hysterectomy) or tubal ligation at least six weeks before taking study treatment. In case of oophorectomy alone, only when the reproductive status of the woman has been confirmed by follow up hormone level assessment.
- Male sterilization (at least 6 months prior to enrolling). For female patients on the study the vasectomized male partner should be the sole partner for that patient.
- Use of oral, injected or implanted hormonal methods of contraception or placement of an intrauterine device (IUD) or intrauterine system (IUS), or other forms of hormonal contraception that have comparable efficacy (failure rate <1%), for example hormone vaginal ring or transdermal hormone contraception. Women using hormonal contraceptives should additionally use a barrier method of contraception.

Note: In case of use of oral contraception, women should have been stable on the same pill for a minimum of 3 months before entering the roll-over protocol.

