- Women are considered post-menopausal and not of child bearing potential if they have had 12 months of natural (spontaneous) amenorrhea with an appropriate clinical

profile (i.e. age appropriate, history of vasomotor symptoms) or have had surgical bilateral oophorectomy (with or without hysterectomy), total hysterectomy, or tubal ligation at least six weeks ago. In the case of oophorectomy alone, only when the reproductive status of the woman has been confirmed by follow up hormone level assessment is she considered not of child bearing potential.

- If a study patient becomes pregnant or suspects being pregnant during the study or within 30 days after the final dose of panobinostat, the Investigator/Study Doctor needs to be informed immediately and ongoing study treatment with panobinostat has to be stopped immediately.
5. Sexually active males unless they use a condom during intercourse while taking the drug during treatment and for 6 months after stopping treatment and should not father a child in this period. A condom is required to be used also by vasectomized men as well as during intercourse with a male partner in order to prevent delivery of the drug via semen.

6 Treatment

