6.1.5 Treatment duration

Patients will continue to be treated until they are no longer benefiting from s.a. oral panobinostat, develop unacceptable toxicities, withdraw consent, are non-compliant with the protocol, the investigator feels it is no longer in the patient's best interest to continue panobinostat therapy (e.g. disease progression, pregnancy, etc.) or the patient dies, whichever comes first. A patient will reach the end of the roll-over study when panobinostat is permanently discontinued. A 30-day safety follow-up should be conducted after the last dose of panobinostat. At every quarterly visit, the investigator is required to confirm that the patient continues to have clinical benefit and may continue receiving study treatment.

The study is expected to remain open for 5 years or until such time that enrolled patients no longer need treatment with s.a. oral panobinostat, whichever occurs first. The study can be terminated at any time for any reason by Novartis.

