7.1 Study flow and visit schedule

Table 7-1 lists all of the assessments and indicates with an "X", the visits when they are performed. All data obtained from these assessments must be supported in the patient's source documentation. Patients must return to the study center at least on a quarterly (every 12 +/- 2 weeks) basis for resupply of study medication. Patients may return to the study center more frequently at the physicians' discretion as clinically indicated or as per standard of care; however, data from these visits will not be captured in the eCRF, but rather only in the source documents at the study center.

The table indicates in the "Category" column which assessments produce data to be entered in the database (D).

[figure not shown]
[figure not shown]

Table 7-1 Visit evaluation schedule

	Category	Protocol reference section	Enrollment	Quarterly (every 12 +/- 2 weeks) visits during treatment phase									End of treatment (EoT)	30 day safety follow-up post last dose of study drug/End of Study
				1	2	3	4	5	6	7	8	9+		
Visit Number			1	2	3	4	5	6	7	8	9+	777	501/778	
Obtain informed consent	D	7.1.2	x											
Parent Study History (e.g. subject's previous study, site and patient number)	D	7.1.2.3	x											
Demography (e.g. gender and date of birth)	D	7.1.2.3	x											
Relevant medical history/current medical conditions	D	7.1.2.3												
Inclusion/exclusion criteria	D	5.2 / 5.3	x											
Adverse events and serious adverse events*	D	8.1.1 & 8.2.2	continuous										x	
s.a. oral panobinostat dosing administration	D	7.1.3	x	continuous										
Pregnancy testing	D, S	7.1.4	continuous											
Confirmation of Clinical Benefit from Study Treatment	D	7.2.1	x	x	x	x	x	x	x	x	x			
End of treatment	D	7.1.5										x		
Study Evaluation Completion	D	7.1.5											x	
*SAEs will be reported to the Novartis safety database within 24 hours of investigator or treating physician's knowledge of the event from the time the patient signed informed consent until at least 30 days after the patient stopped study treatment (see Section 8). Note: All other assessments are performed as per standard of care at the site and will not be captured in the CRF.														

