7.1.4 Pregnancy and assessment of fertility

Since highly effective contraception is required during the study, female patients of child bearing potential are required to test negative for a pregnancy (either with serum testing if routinely/locally available or urine pregnancy test) before enrolling into the study.

Women of child-bearing potential, defined as all women physiologically capable of becoming pregnant, **unless** they are using highly effective methods of contraception during the study and for 3 months after the final dose of panobinostat.

Highly effective contraception is defined as either:

- Total abstinence (when this is in line with the preferred and usual lifestyle of the subject. Periodic abstinence (e.g., calendar, ovulation, symptothermal, post-ovulation methods) and withdrawal are not acceptable methods of contraception.
- Female sterilization (have had surgical bilateral oophorectomy with or without hysterectomy) or tubal ligation at least six weeks before taking study treatment. In case of oophorectomy alone, only when the reproductive status of the woman has been confirmed by follow up hormone level assessment.
- Male sterilization (at least 6 months prior to enrolling). For female patients on the study the vasectomized male partner should be the sole partner for that patient.
- Use of oral, injected or implanted hormonal methods of contraception or placement of an intrauterine device (IUD) or intrauterine system (IUS), or other forms of hormonal contraception that have comparable efficacy (failure rate <1%), for example hormone vaginal ring or transdermal hormone contraception. Women using hormonal contraceptives should additionally use a barrier method of contraception.

If patient has tested negative at the end of study on the parent study, no pregnancy testing is required if enrollment into this study is carried out on the same day or within few days (maximum 5 days) from each other.

Female patients of child bearing potential are required to perform monthly home urine pregnancy tests and complete a simple diary with the dates and the outcome of the home urinary test while on study treatment and during safety follow-up (30 days after the final dose of study medication).

A pregnancy test (either with serum testing if routinely/locally available or urine pregnancy test) on female patients of child bearing potential is required at the final study visit.

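### The consent instruction in Protocol section 11.3 gives women a shorter contraception and fetal-risk period than the 3 months after the last dose required by sections 5.3 and 7.1.4

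*Protocol*

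**What the plan says.** Protocol section 11.3 (Informed consent procedures) has one paragraph for women of child-bearing potential. They are to be warned that study medication "may involve unknown risks to the fetus if pregnancy were to occur during the study", and they are to agree that "they must adhere to the contraception requirement for the duration of the study". The paragraph ends by barring anyone whose reliable compliance is in doubt.

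The contraception rule itself stands in two other places:

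- Section 7.1.4 refers to highly effective contraception "during the study and for 3 months after the final dose of panobinostat".
- Section 5.3, criterion 4, excludes patients unwilling to use it during dosing and for a set time afterwards: "6 months for male participants and 3 months for females) after stopping study treatment".

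The Protocol gives more than one end of study for the individual patient. The last column of Table 7-1 is labelled "30 day safety follow-up post last dose of study drug/End of Study". The Protocol summary says "A patient will reach the end of study when panobinostat treatment is permanently discontinued and the end of treatment visit has been performed". Section 6.1.5 says "A patient will reach the end of the roll-over study when panobinostat is permanently discontinued", and section 7.1.5 is similar. Section 4.3 defines the end of the trial as a whole: 5 years, or all patients off treatment with their 30-day follow-up done, whichever is earlier.

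**The concern.** Section 11.3 tells sites what to say to a woman about fetal risk and what to ask her to agree to. Both statements stop with the study. The rule she has to follow does not: 7.1.4 joins the study period and the 3 months with the word *and*, so the Protocol itself treats the 3 months as additional. A site that followed 11.3 literally would describe a shorter period than the rule.

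This matters most after day 30. The scheduled monthly home pregnancy tests end 30 days after the final dose (7.1.4). The instruction that a patient report a pregnancy covers the study and those same 30 days (5.3). The sponsor-reporting rule in 8.4 concerns pregnancies that occur on treatment. For the rest of the 3 months, adherence depends mainly on what the woman understood and accepted at entry. Section 6.2.5 keeps some patients in contact at 4-week intervals after they stop for an adverse event or abnormal laboratory value, but that does not correct the period stated at consent.

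**Working it through.** The plan gives no figure of its own here, so there is nothing to reproduce. The check compares the periods and then measures the difference in days after the last dose.

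**Step 1. The texts side by side (women)**

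| Place in Protocol | Subject | Period |
|---|---|---|
| 11.3 | Fetal-risk warning | The study |
| 11.3 | Contraception agreement | The study |
| 7.1.4 | Contraception rule | The study plus 3 months after the final dose |
| 5.3, criterion 4 | Willingness required for entry | Dosing plus 3 months after stopping |

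No section defines the study's duration so as to include the 3 months.

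**Step 2. Inputs**

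- Required period after the last dose: 3 months (5.3, 7.1.4).
- Length of a month: 30.4375 days (SAP, Appendix 16.1.9, section 2.2). The SAP gives this for durations in the analysis; using it here is my convention.
- Patient's end of study: 30 days after the last dose (Table 7-1). Section 7.1.7 makes this follow-up mandatory for all patients.

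**Step 3. Calculation**

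- Required days = 3 × 30.4375 = 91.3, about 91.
- Gap = max(0, required days − days from last dose to end of study) = 91 − 30 = 61 days.
- Share of the required period = 61 / 91 = 67%.

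Counting calendar months (89 to 92 days) moves the gap only to between 59 and 62 days.

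**Step 4. Other readings of the end of study**

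- *Literal 6.1.5 and 7.1.5, ending at discontinuation:* 91 − 0 = 91 days (100%). I do not rely on this. Section 6.1.5 itself goes on to ask for the 30-day follow-up, and 7.1.5 places the study completion page 30 days after the end of treatment.
- *Trial-level end, section 4.3:* the gap depends on when she stops.
  - Last dose 91 days or more before the trial ends: 0 days.
  - Last dose 60 days before: 91 − 60 = 31 days.
  - Last patient to stop, trial closing at her 30-day follow-up: 61 days.
  - 5-year limit reached while she is still on treatment: up to 91 days on the letter of 4.3, although 7.1.7 still calls for 30 days of follow-up.

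**Step 5. After the correction**

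If 11.3 covered treatment and 3 months after the last dose, the gap would be 91 − 91 = 0 under every reading.

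**The case against.** The best defence is that 11.3 sets no rule of its own. It refers to the contraception requirement, which 5.3 and 7.1.4 define in full. Criterion 4 cannot be applied without establishing that the woman is willing to use contraception for the whole 3 months. Table 7-1 puts consent and the eligibility check at the same enrolment visit, and 7.1.2 has eligibility assessed once consent is given. What a woman is actually told is in the consent form, which 11.3 describes as a separate document and which the ethics committee reviews with the Protocol (11.2). The study is also small: the Amendment 01 rationale records 9 patients enrolled and 3 ongoing, of either sex and any age.

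Most of this stands, and it limits the consequence. It does not remove the mismatch. After pointing to the requirement, 11.3 attaches its own shorter time limit, and the fetal-risk sentence has no cross-reference that could lengthen it. The 5.3 screen mitigates the problem but leaves the consent instruction saying something different from the rule.

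Three stronger readings are tempting, and the documents do not support them:

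- *Women were told of, or agreed to, only the shorter period.* Nothing shows this. The consent form was not available and may give the 3 months.
- *The whole 3 months is uncovered for each patient.* This takes 6.1.5 and 7.1.5 without the mandatory 30-day follow-up that Table 7-1 labels as the end of study.
- *The same conflict exists for men.* Section 11.3 states no period for men, so there is nothing to conflict with. Criterion 4 already sets 6 months for them, and criterion 5 excludes "Sexually active males unless they use a condom during intercourse while taking the drug during treatment and for 6 months after stopping treatment". A missing sentence for men is an omission, not an error.

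**Conclusion.** The inconsistency is real and is in current text. For women of child-bearing potential, the fetal-risk warning and contraception agreement in 11.3 cover a shorter period than 5.3 criterion 4 and 7.1.4 require. With the patient's end of study at the 30-day follow-up, the wording leaves out about 61 of 91 days. That figure rests on a month of 30.4375 days and on Table 7-1's label for the end of study; under the trial-level definition it can be 0 for a woman who stops well before the trial closes.

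The 61 days measure a difference in wording. They are not a measure of unprotected exposure, and the documents do not say how many women of child-bearing potential are enrolled. The entry screen, and possibly the consent form, reduce the practical risk. This should be corrected because it concerns fetal risk and the correction is easy. It has no bearing on objectives, endpoints, analysis sets or any statistical result.

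**What to change.** Amend the paragraph in 11.3 so that women of child-bearing potential are informed of the fetal risk, and agree to the contraception requirement of 5.3 and 7.1.4, *during treatment and for 3 months after the last dose*. Check that the current consent form states the same period, and correct it if it does not.

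A matching sentence for men (6 months after the last dose, with condom use and not fathering a child, as in 5.3) would be tidy. It is optional and not part of the error.

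The cost is one paragraph, which can go into the next written amendment under 12.1, and a routine check of one document. Data collection and analysis do not change.
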